### Protocol Change Status:

Revision	Date of revision	Reason for amendment
A	10 June, 2016	
B	15 July, 2016	Expanded upper age limit, changes to sample size and statistical analysis plan, additional clarifications and corrections
C	30 March, 2017	Additional clarifications, definitions, and rules required after several run-in cases were performed and site feedback obtained; addition of/change in some assessments (see summary table of changes)

## STUDY OUTLINE

Study Title:	The WISE Trial - Walking Improvement for SCI with Exoskeleton
Sponsor:	Ekso Bionics, Inc. [name] [name]
Study Description:	A randomized, controlled trial comparing exoskeleton gait training with standard gait training or no gait training in community-dwelling participants with chronic incomplete spinal cord injury.
Overall goal:	We aim to demonstrate that Ekso exoskeleton training can significantly improve gait speed in stable chronic, community-dwelling incomplete SCI (iSCI) participants.
Rationale:	Community dwelling iSCI participants may improve clinical gait function by engaging in a gait training regimen, where robotic exoskeletons can readily deliver a dose and simultaneously reduce the physical stress imposed on therapists who use conventional manually assisted stepping practice. Participants receiving exoskeleton training are predicted to show improved function compared to participants receiving no gait training (daily home care), but not superiority to intensity-matched manual gait training. The rationale to implement exoskeleton robotics as preference in gait training is based on high repetition during overground training and reduced therapist burden.
Hypothesis:	Participants undergoing exoskeleton training for 12 weeks /36 sessions will demonstrate equal progress in walking speed as those participants undergoing standard gait training for 12 weeks/36 sessions. Participants in both the exoskeleton group and the standard gait training group will show greater progress after 12 weeks/36 sessions than the participants in the passive control group.
Design:	Multi-center, randomized, controlled study.
Participants:	Chronic ( $\geq 1$ year after the injury), community-dwelling men and women between the ages of 18 and 75 years, inclusive, diagnosed with motor incomplete spinal cord injury (AIS C and D), with minimal walking function, who may benefit from participating in a 12-week (36-session) outpatient rehabilitation therapy and who fulfill the inclusion/exclusion criteria.
	Inclusion criteria:
	

1. Motor incomplete paraplegia or tetraplegia, chronic (<math>\geq 1</math> year after the injury). Non-traumatic SCI injuries can be included, given they are neurologically stable conditions for 12 months (e.g. tumor, transverse myelitis, but NOT Guilliane-Barré)

2. NLI C1- approximately T10 (inclusive, for upper motor neuron injuries only), as determined by the International Standards for Neurological Classification of SCI (ISNCSCI)

3. Sufficient diaphragmatic strength such that respiration is not compromised with exercise.

4. Sufficient upper extremity strength to use a front wheeled walker by manual muscle testing (minimum triceps strength bilaterally of 3/5, shoulder abduction and flexion/extension 4/5)

5. AIS-C SCI & AIS-D SCI, as determined by the International Standards for

Neurological Classification of SCI (ISNCSCI)

6. Ambulates at a self-selected speed of <0.44 meters/second with or without physical assistance and assistance device
7. Able to advance at least one leg forward volitionally with lower extremity muscles (not as a result of trunk movement or spasticity) while using parallel bars, walker or crutches, with or without braces, and with up to 2 people to assist with safety and balance only. Stepping is to be performed by the patient without PT assistance at the lower extremities and no BWS.
8. 18 – 75 yrs old, inclusive
9. No current or history of other neurological conditions
10. Screened and cleared by a physician
11. Involved in standing program or must be able to tolerate at least 15 min upright without signs or symptoms of orthostatic hypotension
12. Weigh 220 pounds (100kg) or less
13. Be able to fit into the Ekso device
14. Between approximately 5'0" and 6'4" tall
15. Standing hip width of approximately 18" or less
16. Have near normal range of motion in hips, knees and ankles

Exclusion criteria:

1. AIS-A SCI or AIS-B SCI
2. Lower motor neuron injuries, as shown by absent reflexes during bilateral quadriceps and Achilles tendon taps
3. < 3 months since previous intensive gait training regimen, FES cycling program, and lower extremity botox injections. The gait training regimen is meant to be formal gait training with feedback for progression of walking (i.e. PT sessions). Participant may have a regular home exercise program and/or a walking exercise program with a companion/ trainer for safety, but not for verbal or tactile cues or feedback regarding gait in the 3 months before initiating the protocol. If participant has a home exercise program and/or a walking exercise program, these programs (except FES cycling) should be continued without changes throughout the protocol. Electrical stimulation devices used regularly for foot drop during ambulation should be considered a brace and should continue to be used as usual throughout the protocol. Upper extremity botox injections are permissible before and during the protocol. One or two PT sessions are allowed to obtain a new brace or progress bracing and check for fit and safety, but no sustained gait training should occur.
4. Already walking at self-selected ambulation speeds of at least 0.44 meter/second with or without assistance
5. Currently involved in another intervention study
6. Concurrent neurological disease
7. Hip flexion contracture greater than ~17°
8. Knee flexion contracture greater than 12°
9. Unable to achieve neutral ankle dorsiflexion with passive stretch (neutral with max 12° knee flexion)
10. Leg length discrepancy
  - a. Greater than 0.5" for upper leg
  - b. Greater than 0.75" for lower leg
11. Spinal instability
12. Unresolved deep vein thrombosis
13. Uncontrolled autonomic dysreflexia
14. Severe muscular or skeletal pain
15. Spasticity that prevents joint motion (severe stiffness or rigidity,) where both

legs have a MAS score of 3 or higher for half or more of their proximal lower extremity muscles; proximal muscles include hip flexors/ extensors/ adductors and knee flexors/extensors.

- 16. Open skin ulcerations on buttocks or other body surfaces in contact with exoskeleton or harness
- 17. Pregnancy
- 18. Cognitive impairments - unable to follow 2 steps commands and communicate for pain or to stop session
- 19. Shoulder extension ROM < 50° excludes crutches during sit to stand or vice versa. (Walking with crutches permitted.)
- 20. Participant requires the assistance of more than one therapist to transfer safely.
- 21. Uncontrolled or severe orthostatic hypotension that limits standing tolerance; defined as sustained, symptomatic drops in systolic and diastolic blood pressure when moving from sitting to standing
- 22. Active heterotrophic ossification (HO), hip dysplasia or hip/knee axis abnormalities
- 23. Colostomy
- 24. History of long bone fractures since the SCI, secondary to osteoporosis
- 25. Unable to sustain current medication regimen, specifically those medications that may impact study outcomes (such as spasticity).
- 26. Any reason the physician may deem as harmful to the participant to enroll or continue in the study

Treatment Groups: **Run-In Group:** The first 1 to 4 Participants at each site will be assigned to the Run-in Group. The Run-in Group follows the Group 1 assignment described below. After the site has completed the Run-in phase, Participants who meet study entrance criteria will be randomized to one of three groups:

**Group 1:** Ekso Intervention - Participants in this group receive Ekso GT robotic gait training 3 times per week for 12 weeks (36 sessions). The goal is a minimum of 300 steps of gait training in the Ekso GT per 45 minute session. Overground walking starts when Participants require only minimal assistance of one therapist and one aide to assist with assistive device, without any BWS, for at least 10 meters. This will be assessed every 3rd session during the 10MWT. At this point, sessions will consist of 30 minutes of gait training in the Ekso, followed by 15 minutes of standard overground gait training without BWS for a total of 45 minutes of walking. See Table I A for the training progression strategy and section 10 – Training Regimen and Rules for details.

**Group 2:** Active controls - Participants in this group receive a matched number of sessions of standard gait training. Sessions will consist of 45 minutes of walking 3 times per week for 12 weeks (36 sessions). Standard gait training will be a combination of body-weight supported treadmill training and overground training without BWS, with a goal of a minimum 300 steps during BWSTT per session. Overground walking starts when Participants require only minimal assistance of one therapist and one aide to assist with the assistive device, without any BWS, for at least 10 meters. This will be assessed every 3rd session during the 10MWT. Once the overground criterion is achieved: If the initial 300 steps **are not completed** by the end of the first segment, the middle 15-minute segment must be gait training in BWSTT, and the final 15-minute segment must be OG gait training. If the initial 300 steps **are completed** by the end of the first segment, the middle 15-minute segment can be continued gait training in BWSTT or OG gait training, per PT choice. The final 15-minute segment must be OG gait training. See Table 1 B for the training progression strategy and section 10 – Training Regimen and Rules for details.

**Group 3:** Passive controls with cross-over option - Participants in this group continue with daily activities as normal over 12 weeks. No new gait training, mobility therapy, nor new medications (including Botox) are commenced during the study period. Participants in this group will come to the study sites for evaluations at baseline, 6 and 12 weeks. After the 12 week evaluation, the participants in this group will have an opportunity to choose to receive either Ekso or standard gait training therapy for 12 weeks.

Sample Size: Up to 40 Run-In Participants and up to 127 total Randomized Participants; Randomization by groups is 2:2:1.

Blinding: Outcomes data will be collected by independent, blinded evaluators trained in standard assessment techniques.

Setting/Sites: Outpatient Rehabilitation Setting involving up to 15 clinical sites. Sites to be chosen based on having Ekso Level 2 training certification, ability to match manual therapy regimen prescribed by this protocol, location, enrollment capabilities, and resources.

Duration: Each randomized Participant is expected to engage in this study for approximately 6 months. Run-in Participants are expected to be active in the study for approximately 14 weeks. The duration of the study is expected to be approximately 3 years.

Assessment periods:	The study consists of a screening/pre-evaluation period, a 12 week training period (36 sessions) with limited weekly assessments (every 3 rd session) for safety/progression measures, and full evaluations at the end of training weeks 6 (midpoint/following session 18) and 12 (endpoint/following session 36). Randomized Participants are to return 3 months after the last training session (follow up) at which time they will undergo the same full evaluation as training weeks 6 and 12. Assessments are to be performed outside of exoskeleton or any body weight support.
Primary Objective:	To demonstrate that a 12 week robotic gait training regimen can lead to a clinically meaningful improvement in independent gait speed on the 10 Meter Walk Test (10MWT) in community dwelling participants with chronic iSCI.
Secondary Objectives:	
To examine the economic factors such as number of physical therapists/staff required during training.
 
To analyze the physical burden on therapists assisting and supervising during training.
 
To study the influence of factors that may modify the gait recovery in the chronic incomplete SCI population (demographic, clinical, functional, psychological, balance, etc.)

Primary End Point:	The primary endpoint is the mean increase in gait speed demonstrated during the 10MWT after 12 weeks/36 sessions of training and compared between groups. Both self-selected and fast speeds will be performed on the 10MWT, with the fast speed taking precedent.
Secondary Endpoints:	Participant outcomes related to physical performance, physiology, quality of life, and safety are to be measured at weeks 6 / following session 18 (midpoint), week 12/ following session 36 (endpoint), and week 24 /3 months after the last sessions (follow-up) (unless otherwise indicated) and compared between groups. By category, these are the following:

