### **4. Study Endpoints**

The primary and secondary endpoints are as follows:

The primary endpoint is the mean increase in gait speed demonstrated during the 10MWT after 12 weeks/ 36 sessions of training and compared between groups. Both self-selected and fast speeds will be performed on the 10MWT, with the fast speed taking precedent.

The secondary endpoints of Participant outcomes related to physical performance, physiology, quality of life, and safety are to be measured at week 6/following 18 sessions (midpoint), week 12/following 36 sessions (primary endpoint), and week 24/3 months after the last session (follow-up) (unless otherwise indicated) and compared between groups.

By category, these are the following:

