This study design involves outcome variables measured on binomial, ordinal, and continuous scales. For the continuously scaled outcome variables (i.e., 10MWT, 6MWT, WISC-II Score, etc.), the general situation applies analysis of variance and covariance when there are  $g$  distinct groups with a sample of observations for each group. The general null hypothesis is that the outcome variable distribution is the same for the treatment and the active control group. The assumptions associated with the analysis of variance are: 1) the  $g$  samples are independent random samples, 2) the observations in group  $i$  (for each  $i = 1, 2, \dots, g$ ) are a random sample from a normal probability distribution with mean  $\mu_i$  and variance  $\sigma_i^2$ , and 3) the  $g$  population variances,  $\sigma_1^2, \dots, \sigma_g^2$ , are equal to a common variance  $\sigma^2$ . Inherent to these assumptions is the assumption of a linear additive model with equal sample sizes. There are a variety of statistical procedures for the comparison of means in an analysis of variance setting. In the case of unequal sample sizes and multiple endpoints, the Scheffe's or Bonferroni procedures are appropriate to control for experiment-wise multi-comparison error (Woolson, 1983). If the assumption of normal distributions is not met, rank analysis of variance is used. More common rank analysis of variance tests are Kruskal-Wallis and Friedman tests. In addition, paired t-Test will be used for paired data since this is a single group matched-pairs design with the assumption that the pairwise differences are normally distributed.

Multiple comparison analysis (repeated measures) of ordinal or nominal-scale data (i.e., 5-point Likert type scales, numeric rating scales, etc.) generally assumes a logit model. This type of model uses cumulative logits, which automatically take the ordinality of the data into account. If the assumptions associated with this model are met, tests of uniform association and proportional odds can be computed. If, however, maximum likelihood estimation is desirable, generalized logits are computed from a log-linear model (Agresti, 1990 and Stokes et al., 1995).

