## 1.2 Working Study Hypotheses

Participants undergoing exoskeleton training for 12 weeks /36 sessions will demonstrate equal progress in walking speed as those participants undergoing standard gait training for 12 weeks/36 sessions. Participants in both the exoskeleton group and the standard gait training group will show greater progress after 12 weeks/36 sessions than the participants in the passive control group.

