#### **1.6 Multiplicity**

Although there is only one efficacy study endpoint and one safety study endpoint, the assessment of primary and secondary endpoints as well as the repeated measurement of the primary efficacy endpoint over time warrants the implementation of a conservative alpha allocation strategy. Common methods for handling endpoint multiplicity as suggested by Bonferroni and Tukey are useful adjustments for establishing significance levels and hypothesis testing (Hochberg et al). Moreover, a hierarchical test procedure (i.e., fixed sequence procedure) will be followed in order to reflect the relative clinical importance of the null hypothesis for the primary and secondary endpoints. The fixed sequence procedure tests hierarchically ordered hypothesis in sequence until at a 0.05 significance level until first non-rejection. Once a hypothesis is not rejected, no further testing will be performed. It is assumed that

the overall study hypothesis is more important than the primary and secondary endpoint hypotheses and the primary endpoint hypotheses are more important than the secondary endpoint hypotheses.

All analysis will be performed using SAS Analytics Pro, Version 9.3 and JMP Statistical Software, Version 13.2 (SAS Institute Inc., Cary, NC or MedCalc Statistics for Biomedical Research, Version 18.1, MedCalc Software, Belgium, EU.

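### For continuous secondary outcomes the SAP writes only an Ekso-versus-active equality null, puts it in a stop-at-first-failure sequence, and specifies no test against passive control

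*Protocol*

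**What the plan says.** Four parts of the plan have to be read together.

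- **Prediction.** The rationale in the Protocol's Study Outline says that exoskeleton participants are "predicted to show improved function compared to participants receiving no gait training (daily home care), but not superiority to intensity-matched manual gait training". Protocol section 2 also predicts no superiority over manual training. SAP 1.2 adds a sentence whose comparator, named at its end, is passive control: "Participants in both the exoskeleton group and the standard gait training group will show greater progress after 12 weeks/36 sessions than the participants in the".
- **Null for continuous outcomes.** SAP 1.1 names the 10MWT, 6MWT and WISCI-II as examples and states: "The general null hypothesis is that the outcome variable distribution is the same for the treatment and the active control group". The same paragraph says that "the general situation applies analysis of variance and covariance when there are" several distinct groups, and mentions Scheffé, Bonferroni and rank methods. It names no other pair of arms. Protocol section 4 closes its list of secondary visits with "follow-up) (unless otherwise indicated) and compared between groups", again without naming pairs.
- **Sequence.** SAP 1.6 says: "The fixed sequence procedure tests hierarchically ordered hypothesis in sequence until at a 0.05 significance level until first non-rejection". It continues: "Once a hypothesis is not rejected, no further testing will be performed". It ranks the overall study hypothesis first, then primary, then secondary endpoints, and gives no order within the secondaries.
- **Primary endpoint.** SAP 1.3 and Protocol 17.2 test Ekso for superiority over passive control on 10MWT change, and compare Ekso with active control using a 0.055 m/s margin.

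**The concern.** The one contrast written down for continuous secondaries is the one on which the trial predicts no advantage for Ekso. A difference test on that contrast is expected not to reject, and under SAP 1.6 a non-rejection ends all further testing. The contrast on which the trial does predict a gain, trained against untrained, has no written hypothesis for any continuous secondary and so no place in the sequence.

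At stake is any confirmatory statement that Ekso improves function over no training on a continuous measure other than the primary. Therapist burden could be cut off as well. The outline gives reduced burden as a reason to prefer the device, and nothing says whether those outcomes come before or after the participant measures.

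**Working it through.** **Inputs** (Protocol 17.4 and SAP 1.8, change in gait speed in m/s):

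| Arm | Mean | SD | Evaluable n |
|---|---|---|---|
| Ekso | 0.11 | 0.18 | 38 |
| Active control | 0.078 | 0.108 | 38 |
| Passive control | 0 | 0.108 | 19 |

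Protocol 17.1 makes superiority tests two-sided at 0.05 and non-inferiority tests one-sided at 0.05. No effect size or SD is given for any secondary outcome, so the 10MWT values stand in for them. This is an assumption. Power is from the noncentral t with Welch degrees of freedom unless stated otherwise.

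**Step 1: reproduce the plan's sample sizes.**
- Superiority over passive control: SE = √(0.18²/38 + 0.108²/19) = 0.0383, and 0.11/0.0383 = 2.87. Power is 80.5% (81.9% by normal approximation). The smallest 2:1 design reaching 80% is 38/19, as stated.
- Non-inferiority to active control: true difference 0.032 and margin 0.055, so the distance is 0.087. At 37 per arm, SE = √((0.18² + 0.108²)/37) = 0.0345. Power is 80.3% by the t method with 2n − 2 degrees of freedom, so 37 per arm is reproduced.

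**Step 2: a difference test of Ekso against active control.**
- Arms equal: the rejection rate is the test level, 5%. This needs no stand-in values.
- Planning gap, 0.11 − 0.078 = 0.032: at 38/38, SE = √((0.18² + 0.108²)/38) = 0.0341, and 0.032/0.0341 = 0.94. Power is 15.2%.
- If all 127 randomized were evaluable, 127 × 2/5 ≈ 51 per arm: SE = 0.0294, ratio 1.09, power 19.0%. This is an upper case, because part of the excess over 95 is there to cover attrition.

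Such a test, when reached, therefore fails and closes the sequence in about 95% of trials (arms equal), 85% (planning gap, 38/38) or 81% (planning gap, 51/51).

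**Step 3: the same outcome tested as Ekso against passive control.** On the stand-in values this is the superiority calculation in Step 1: 80.5% at 38/19.

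**Step 4: the alternative reading, a three-group overall test.** In 20,000 simulated trials at 38/38/19 with the planning SDs, the one-way F test rejects 68% of the time at the planning means, and 81% if both trained arms gain 0.11. At 51/51/25 and the planning means it rejects 82%. This reading would usually pass, but a significant F does not say which arms differ.

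**The case against.** The strongest reply is that one generic sentence in SAP 1.1 is being made to carry too much. The paragraph is about several groups. Its remark on unequal sample sizes makes sense only if passive control is included, since Ekso and active control are planned equal. It lists the 10MWT, for which SAP 1.3 gives different hypotheses, so the sentence plainly does not exclude other contrasts. This stands as far as it goes: passive control is not ruled out for the secondaries. But a fixed sequence needs each hypothesis named in advance, and the only one named is against active control. General wording about groups does not supply the missing one.

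A reader might infer that the predicted gain over passive control is never tested. The documents do not support that: it is the first primary hypothesis, ahead of every secondary. Nor does the gap extend to binary outcomes, for which the SAP 1.1 null of no association is not limited to active control.

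A reader might also infer that equal progress in walking speed would be claimed from a non-significant difference. It would not, because that claim rests on the 0.055 m/s margin.

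Finally, one might say that secondary testing will end at its first step in 95% of trials. That cannot be said. SAP 1.6 gives no order, so the first secondary could be a binary or therapist outcome, and the overall and primary hypotheses must pass beforehand.

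**Conclusion.** The point holds for continuous secondary outcomes. The written null is on the contrast where the trial predicts no superiority, no hypothesis against passive control is specified for these outcomes, and the stopping rule turns the expected non-rejection into a block on whatever follows. When such a test is reached, its chance of rejecting is 5% if the arms are equal, and 15% at 38/38 (19% at 51/51) at the planning gap, against about 80% for Ekso versus passive control at 38/19.

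Only the 5% is free of the assumption that secondary outcomes have standardised effects like those of the 10MWT. The primary hypotheses are unaffected. The change should be made because confirmatory secondary claims depend on it.

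**What to change.** In SAP 1.1, for the continuous participant secondaries that enter the sequence, state the null as Ekso versus passive control at week 12, tested for superiority at two-sided 0.05. Week 12 is the last usable visit, because Protocol Table 2 gives Group 3 no later evaluation. For the same outcomes, report Ekso versus active control as a difference with a 95% confidence interval, outside the sequence.

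In SAP 1.6, list the sequenced secondaries in an order fixed before the data are seen, and say where therapist burden (Ekso versus active control) sits. Which outcomes to include and in what order is the sponsor's choice.

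This is a change of SAP wording only, with no added patients, visits or data. The cost is that no formal secondary efficacy test against active control remains for these outcomes, on a contrast where the trial itself predicts no superiority.
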